#### 6.2.2 Exclusion criteria

- ✓ Vulnerable subject with regard to the current regulation
  - Pregnant, parturient or breast-feeding woman;
  - Subject deprived of freedom by judicial, medical or administrative decision;
  - Under age subject;
  - Subject is legally protected or unable to express his/her consent;
  - Subject not affiliated with or not a beneficiary of a social security scheme;
  - Subject falling into several categories above;
- ✓ Subject who refused to participate in the study
- ✓ Subject participating in an interventional clinical study
- ✓ Subject who, according to the investigator, has cognitive problems that prevent him/her from completing a questionnaire or for whom the assessment may be a problem.

### 6.3 Investigators

The investigators participating in this study will primarily be urologists or doctors in physical medicine and rehabilitation. Approximately fifty investigators are expected to recruit the 250 patients expected for the study. These sites will be located throughout France.

## 7 STUDY IMPLEMENTATION

### 7.1 Inclusion

The study is for people who are newly educated in ISC and who have chosen to use a catheter from the SpeediCath range after they have completed their self-catheterisation training. It will be conducted with approximately fifty investigator sites. To ensure good representativeness, the number of patients/sites will be limited to five.

In order to limit selection bias, investigators should propose, if possible, study participation to all eligible patients who are seen consecutively. Screened eligible patients will have been informed of the study and will have wanted to participate in it (non-opposition).

After verification of the screening criteria, informing the patient will be carried out. At the end of this step, and in the absence of patient opposition, a patient identification number will be assigned to him/her and will be used throughout the study.

### 7.2 Participation in the study

The subject's participation in the study does not involve any additional examinations compared to the usual management of a patient. The study will be offered to subjects until the threshold headcount is reached at each site or until the total headcount is reached.

Since the study is observational, patients are free to make the decision to change catheters during follow-up if the initially chosen catheter is not suitable for them. In this case, this change will be documented as well as the model and brand of the new catheter chosen and the patient will continue the study normally.

### 7.3 Withdrawal from the study

Enrolled patients who meet at least one of the following criteria will be withdrawn from the study:

- Participant opposed to continuing the study,
- Participant who stopped self-catheterisation.

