1 SYNOPSIS

Title	STUDY OF SPEEDICATH CATHETER SELECTION CRITERIA AT THE START OF SELF-CATHETERISATION
Short title	Eva
Sponsor	COOPLAST
Coordinator	[name]
Trial type	Multicentre observational study
Objectives	
Primary objective:          Specify the final choice criteria for the type of SpeediCath (SC) catheter that provides patient satisfaction determined by self-questionnaire at V3
 
Secondary objectives:
 
 
- Document the reasons for the patient's initial choice of the SC catheter: determined by self-questionnaire at V1
 
- Determine the patient's adherence to Intermittent Self-Catheterisation (ISC) at the end of follow-up and his/her development over the first six months: measured by I-CAS at V2 and V3
 
- Document patient satisfaction with the catheter: measured on a five point scale at V2 and V3
 
- Document challenges during the first six months of the ISC: measured by the IC-Di-Q at V2 and V3
 
- Determine the variables associated with the catheter selection and adherence to the ISC.
 

Eligibility criteria	
Inclusion criteria
 
 
• Female or male aged eighteen years or older
 
• Subject informed of the study and who decided to participate in it (non-opposition)
 
• Subject affiliated with a social security scheme or beneficiary
 
• Subject with neurogenic or non-neurogenic bladder issues, justifying the implementation of ISC to empty the bladder
 
• Subject who received his/her initial ISC training at the time of inclusion
 
• Subject for whom the expected ISC duration is at least six months
 
• Subject for whom at least two types of SC catheters have been introduced and who has chosen to use the catheters from the SpeediCath range as the first catheter for self-catheterisation
 
• Subject able to independently conduct ISC
 
• Subject for whom the healthcare professional has recommended to conduct ISC at least four times per day
 

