2 STUDY FLOWCHART

V1 - Screening Visit – Inclusion D0		
	Investigator	Patient information
		Inclusion and non-inclusion criteria
		Socio-demographic data
		Clinical data and scores
		Acceptance of the ISC (I-CAT)
		Concomitant bladder treatments
		Method for choosing the catheter and the patient's criteria for choosing the catheter
		Education conditions and ISC methods
		Adverse events
V2 - Follow-up visit - 3 to 12 weeks		
	Investigator	Clinical data
		Continuation of ISC
		Continued use of chosen catheter
		Concomitant bladder treatments
		Adverse events
	Patient	Daily frequency of the ISC
		Overall impression with the ISC
		Satisfaction with the catheter (on a five point scale)
		Challenges during the ISC (IC-Di-Q)
		ISC adherence (I-CAS)
V3 - End of study visit – around 6 months		
	Investigator	Clinical data
		Continuation of ISC
		Continued use of chosen catheter.
		Concomitant bladder treatments
		Adverse events
	Patient	Daily frequency of the ISC
		Overall impression with the ISC
		Satisfaction with the catheter (on a five point scale)
		Patient's final choice criteria for the catheter
		Challenges during the ISC (IC-Di-Q)
		ISC adherence (I-CAS)

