### 4.2 Secondary objectives

The secondary objectives are as follows:

- Document the criteria for the patient's initial choice of the SC catheter: determined by self-questionnaire at V1
- Document patient satisfaction with the SC catheter: measured on a five point scale at V2 and V3
- Document the challenges encountered during the first six months of the ISC: measured by the IC-Di-Q at V2 and V3
- Determine patient adherence to the ISC over the first six months: measured by I-CAS at V2 and V3.
- Determine the variables associated with the catheter selection and adherence to the ISC.

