## 9.2 Statistical analysis

The analyses will be performed using the SAS V9.4 software (or earlier version), on a frozen database, after review of data allowing to identify protocol deviations and their potential impact on the analysis criteria. Protocol deviations will be classified as minor or major. Major deviations will lead to the exclusion of patients from the per protocol (PP) population. The distribution of patients in the analysis populations will be reviewed and approved by the sponsor before the database freeze.

The description of all the parameters will be based on the type of catheter and according to the gender of the patients. Quantitative parameters will be described using the following statistics: number of non-missing data, mean, standard deviation, median, first and third quartile, minimum and maximum. Qualitative parameters will be described using the headcounts and the percentages. These will be calculated from the number of non-missing observations. In all cases, the number of missing data will be specified.

Univariate analyses then multivariate analyses by logistic regressions will be performed to identify, among the data studied (patient choice criteria at V1, his/her final choice at V3, his/her adherence to ISC, his/her satisfaction with the catheter, his/her challenges during ISC, his/her clinical and socio-demographic characteristics, etc.), the predictive factors of the final choice of the SpeediCath catheter (Standard, Compact or Flex for male patients; Standard, Compact or Compact Eve for female patients).

The same will be done for adherence to ISC at V3 (with clinical and socio-demographic characteristics at V1, I-CAT score at V1, ICDQ score at V2, type of catheter chosen).

The other secondary endpoints will be described at the different time points and according to the catheter type.

Missing data at the time of analysis will not be replaced and will be considered as such.

A statistical analysis plan will be written after approval of the protocol. This document will have a reference value for the statistical analyses.

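### Patients who stop self-catheterisation are withdrawn from the study, so those known to have stopped before V3 drop out of the V3 adherence results because of the outcome itself

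*Protocol*

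**What the plan says.** Section 7.3 opens with a mandatory rule, "Enrolled patients who meet at least one of the following criteria will be withdrawn from the study", and gives two criteria: opposition to continuing, and "Participant who stopped self-catheterisation". No exception is made for the second.

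Adherence is nevertheless something the study sets out to measure. The Synopsis lists "adherence to Intermittent Self-Catheterisation (ISC) at the end of follow-up and his/her development over the first six months" among the secondary objectives, and section 4.2 has "Determine patient adherence to the ISC over the first six months: measured by I-CAS at V2 and V3". After describing the logistic regressions for final catheter choice, section 9.2 adds: "The same will be done for adherence to ISC at V3". The predictors include V1 characteristics, the I-CAT score, V2 difficulties and catheter type.

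On incomplete data, section 9.2 says of percentages "These will be calculated from the number of non-missing observations", and in general "Missing data at the time of analysis will not be replaced and will be considered as such".

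The Study Flowchart lists "Continuation of ISC" as an investigator item at both V2 and V3. Section 8 adds information about stopping, where applicable, at the same two visits. It specifies neither a date nor a reason.

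**The concern.** Giving up ISC is plausibly the extreme of non-adherence. A rule that removes such patients from the study lets the outcome decide who is analysed for that outcome. Entry requires an expected ISC duration of at least six months (section 6.2.1), so stopping before V3 runs against the expectation at entry. Some patients will still stop because they no longer need ISC, and they must be told apart from those who gave up.

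The rationale in section 3 says that little is known about what helps or hinders adherence in the first six months, and section 4 intends the results to guide counselling. If a V1 characteristic or a catheter type makes patients give up, and those patients are then absent from the model, the association can be missed or distorted.

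Section 7.3 also fits poorly with section 8. Stopping is both an item to record and a reason to leave. It is unclear whether a patient first found at V3 to have stopped is documented there or simply withdrawn. By contrast, section 7.2 keeps patients who change catheter in the study.

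**Working it through.** **The plan's own figure.** Section 9.1 states a precision of ±2.75% to ±6.25% with 250 patients, and ±3.0% to ±6.5% if 10% of final choice criteria are not recovered. With 1.96·√(p(1−p)/n) at p = 5% and 50%, the half-widths are ±2.70% and ±6.20% at n = 250, and ±2.85% and ±6.53% at n = 225. The stated figures reproduce, and the sample size is not in dispute.

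**How the rule acts.** A patient known before V3 to have stopped is withdrawn (7.3) and so has no V3 I-CAS. The missing score is not replaced, and the patient is outside the denominator (9.2). Nothing in the protocol follows withdrawn patients to V3 or counts a stopper as non-adherent.

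**Inputs for the size.** The protocol gives no stopping rate and no I-CAS cut-off. The 10% in section 9.1 gives loss to follow-up and consent withdrawal as its examples, so it is not used as a stopping rate. All of the following are assumed, for a yes/no adherence outcome such as a logistic regression needs:

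- p = share of persisters who are adherent
- s = share of patients who stop ISC
- f = share of stoppers who gave up; the rest no longer needed ISC and are outside the denominator
- k = share of stoppers lost from the V3 analysis because they were known and withdrawn earlier

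**Formulas.** With stoppers counted: p(1−s) / (1−s+f·s). As planned: p(1−s) / (1−s+(1−k)·f·s). The overstatement is planned minus counted.

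**Worked case, p = 0.70 and s = 0.10**, so p(1−s) = 0.63:

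- f = 1, k = 1: 0.63/0.90 − 0.63/1.00 = 70.0% − 63.0% = 7.0 points
- f = 0.5, k = 1: 0.63/0.90 − 0.63/0.95 = 70.0% − 66.3% = 3.7 points
- f = 1, k = 0.5: 0.63/0.95 − 0.63/1.00 = 66.3% − 63.0% = 3.3 points
- f = 0.5, k = 0.5: 0.63/0.925 − 0.63/0.95 = 68.1% − 66.3% = 1.8 points
- f = 0 or k = 0: 0

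**Overstatement in points, p = 0.70:**

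| | s = 5% | 10% | 15% | 20% |
|---|---|---|---|---|
| f = 1, k = 1 | 3.50 | 7.00 | 10.50 | 14.00 |
| f = 0.5, k = 1 | 1.79 | 3.68 | 5.68 | 7.78 |
| f = 1, k = 0.5 | 1.71 | 3.32 | 4.82 | 6.22 |
| f = 0.5, k = 0.5 | 0.89 | 1.79 | 2.72 | 3.66 |

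For p from 0.60 to 0.80 and s from 5% to 20%, the ranges in the same row order are 3.0–16.0, 1.5–8.9, 1.5–7.1 and 0.8–4.2 points. For scale, the 95% half-width at 70% is 1.96·√(0.7·0.3/250) = 5.7 points, or 6.0 at n = 225.

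**Regression.** Take two groups with 70% of persisters adherent in each, and 5% versus 20% stopping.

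- f = 1, stoppers counted: 66.5% v 56.0%, OR = (0.665/0.335)/(0.560/0.440) = 1.56
- f = 1, half lost: 68.2% v 62.2%, OR 1.30
- f = 1, all lost: 70% v 70%, OR 1.00
- f = 0.5: OR 1.30 counted, 1.16 with half lost, 1.00 with all lost

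**The case against.** The strongest reply is that withdrawal does not delete what is already on file. Continuation and stopping are recorded at V2 and V3, section 9.2 promises a description of all parameters, and an SAP could define adherence so that recorded stoppers count as non-adherent. The loss would then depend on how the outcome is coded. This stands in part: for a stopper recorded at V2, status alone would be enough. But section 9.2 says nothing of the kind, and an SAP cannot recover follow-up that a conduct rule has ended. Nor can it separate giving up from no longer needing ISC if the reason was never collected.

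Second, one can read the visit at which stopping comes to light as documenting it before withdrawal takes effect. At V3 that costs no later visit, and the protocol schedules no contact between V2 and V3, so many stoppers may surface only at V3. That is fair and is why k below 1 is shown. Even so, the k = 0.5 rows are generous to the plan, because they count stoppers found at V3 as non-adherent, which the protocol does not say.

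Third, every input is assumed, and the 7.0-point figure and the odds ratio of 1.56 need unfavourable combinations. That stands: the figures show a mechanism and a range, not an estimate.

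Fourth, adherence among continuing users is a legitimate quantity. It is, but it should be labelled as such and shown beside the result for all patients who still needed ISC. Finally, date and reason of stopping may already be on the eCRF, so naming those fields in the protocol is detail.

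**Conclusion.** The concern holds. Followed as written, section 7.3 together with section 9.2 removes patients known to have stopped before V3 from the V3 adherence description, the V2-to-V3 change and the V3 adherence regression, and does so because of the outcome. Any V2 I-CAS already collected is kept.

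The size cannot be derived from the protocol. Over the assumed range it runs from 0 (no stopper gave up, or all are documented and counted) to 16.0 points (80% of persisters adherent, 20% stopping, all gave up, all lost). In the case with 70% of persisters adherent and 10% stopping it is 1.8 to 7.0 points, against a sampling half-width of 5.7. A real association can be reduced to an odds ratio of 1.00. None of these figures applies to the 0–8 I-CAS score itself.

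The point concerns secondary objectives in an exploratory study. For the final choice criteria and the IC-Di-Q, restriction to current users is largely inherent and only needs stating. It should be fixed; confidence is medium.

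**What to change.** - **Section 7.3:** keep opposition as the reason for study withdrawal, and treat stopping ISC as a recorded study outcome.
- **Sections 7.3 and 8:** reconcile them by stating that a patient who has stopped is still documented at V2 and V3 where usual follow-up allows. Name date and reason within the stopping item.
- **Section 9.2, stopping:** report the proportion who stopped among patients with known ISC status, and show the number of unknown status. For example, with 23 known stoppers and 25 of 250 unknown, 23/225 = 10.2%, whereas 23/250 = 9.2% would treat the unknowns as continuing.
- **Section 9.2, V3 adherence:** count those who gave up as non-adherent, report those who no longer needed ISC separately and outside that denominator, and give the persisters-only result alongside.
- **Other V3 questionnaire results:** state that they are conditional on continuing ISC.

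The cost is wording in 7.3, 8 and 9.2, plus two fields within an item already listed. No examination is added, and clinical decisions about stopping ISC are not touched. Three limits remain. Section 3 describes the routine second visit as taking place after six months of use, so some stoppers may not be seen. The reason for stopping will sometimes be uncertain. Reported adherence will look less favourable.

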## 8 COLLECTED DATA

### Screening and inclusion visit

During this visit, the following data will be recorded in the case report form:

- Unique identifier number;
- Date of visit;
- Patient's socio-demographic data: gender, age, living alone or with someone, professional activity, level of education
- Patient's clinical data: pathology and degree of involvement, history (age of bladder issues, bladder clean out mode, urinary symptoms (USP score), concomitant bladder treatments), anorectal dysfunction (considering the impact of these disorders on vesico-sphincter balance), accessibility of urinary meatus (manual dexterity, upper limb joint range of motion, mobility, limitation of lower limb abduction in women, vision disorders, obesity, overweight with significant apron belly, prolapse in women), urethral sensitivity (normal/decreased/increased)

- Acceptance questionnaire for I-CAT ISC
- Choice of catheter: catheters presented by the nurse, catheters tried by the patient, SpeediCath (SC) catheter chosen by the patient as the first catheter for self-catheterisation and the criteria that presided over this choice
- ISC learning terms and conditions: location, duration, number of trainings in the procedure, prescription of home nursing representative
- Recommended frequency for ISC
- ISC alone or associated with spontaneous urination
- Possible adverse events
- Date of next visit

**Follow-up visit at three to twelve weeks**

- Date of visit;
- Patient's clinical data. Urinary symptoms (USP score). Concomitant bladder treatments
- Self-catheterisation: methods of use, continuation of self-catheterisation, information on stopping, if applicable
- Catheter chosen: continue self-catheterisation with the chosen catheter or catheter change, information on the catheter change, if applicable
- Patient questionnaire on catheter use and satisfaction (on a five point scale),
- IC-Di-Q
- I-CAS
- Possible adverse events
- Date of next visit

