### 3 STUDY RATIONALE

Urinary self-catheterisation involves emptying your bladder on your own by inserting a catheter into the urethra. This is the standard method in the case of dysfunctions of the **bladder** clean-out phase, **particularly in the case of complete urinary retention or complete or incomplete bladder clean-out with subvesical obstruction**. Neurological conditions such as spinal cord injuries, multiple sclerosis, multiple system atrophy, peripheral neuropathies, or Parkinson's disease and stroke can cause bladder disturbances. These disturbances can also result from pelvic denervations that are consequences of extended pelvic surgeries or radiation therapy intended for the treatment of gynaecological, urological or digestive cancers.

The goal of ISC implementation is to reduce the morbidity related to vesico-sphincter dysfunction and improve the quality of life of patients by making them more independent.

It involves for the patient a rigorous learning phase and an acceptance phase of this new micturition mode.

When intermittent self-catheterisation (ISC) is indicated, training is provided to the patient in order to enable him/her to manage the catheterisation on a daily basis. The objectives of this study are to understand, achieve, monitor and adapt self-care. This training, primarily provided by the nursing staff and/or a specialist doctor, is usually ensured during an admission to hospital. After returning home, the patient continues to be monitored by the specialist doctor and the nursing team to assess the mastery of the technique (possibly review the procedure and ensure the suitability of the catheter), patient adaptation to ISC practice, his/her compliance with the associated rules (frequency and regularity of catheterisations, urine volume) and any complications. A first visit is usually performed between three and twelve weeks, then a second visit after six months of use.

But this patient therapeutic education (PTE), even performed by experienced and specifically trained staff, may not be sufficient for the patient's immediate acceptance and his/her adherence to self-catheterisation in the medium or long term.

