To date, there is no objective data to help in the choice of the type of catheter to offer to the patient based on his/her needs. Although it is now known that the quality of life of patients practising ISC is dependent on multiple factors, there is little data on factors that facilitate or hinder adherence to ISC during the first six months, post-initiation to ISC. The exploratory multicentre prospective observational study we want to conduct aims to determine which criteria are the patient's choice in terms of SC catheters. This information would allow in the future to be able to implement personalised advice with each patient, with the aim of offering them the SC catheter that best suits his/her needs. The study population will consist of adults with neurogenic or non-neurogenic bladder issues justifying the implementation of ISC, with ISC education occurring at the time of inclusion. Patients should be independent in the practice of ISC, and the minimum expected duration of follow-up should be greater than or equal to six months. Only patients who choose to use catheters from the SpeediCath range will be included in the study.

Many criteria will be collected to allow for a thorough analysis of the methods for choosing the type of SC catheter. This collection involves the use of patient self-questionnaires. These questionnaires will be collected during the patient's usual follow-up, including a visit at the time of ISC education, a follow-up visit around three to twelve weeks (depending on the investigator site practices) and a second follow-up visit around six months.

- ✓ ISC acceptance will be measured by the "Intermittent Catheterisation Acceptance Test" (I-CAT) questionnaire. This is a patient questionnaire developed by the French Language Neuro-Urology Study Group (GENULF) and validated in French in 2016 in a multicentre prospective study conducted in 201 neurological and non-neurological patients. The I-CAT helps to better assess and understand the psychological barriers that patients face in relation to ISC. The questionnaire consists of fourteen questions, with a minimum score of 0 for perfect acceptance, and the maximum score of 56 characterises the worst possible acceptance.

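### V2 scores taken anywhere from 3 to 12 weeks after training are treated as one time point, and the V3 adherence model uses the V2 difficulty score without its timing

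*Protocol*

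**What the plan says.** Protocol section 8 labels the second visit "Follow-up visit at three to twelve weeks". Section 3 describes it as "a follow-up visit around three to twelve weeks (depending on the investigator site practices"), and explains the window by usual care: "A first visit is usually performed between three and twelve weeks, then a second visit after six months of use". Initial training takes place at inclusion (section 6.2.1), so the window is also the range of time since training. V3 is placed at around six months for everyone (section 2).

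Satisfaction, IC-Di-Q and I-CAS are all collected at V2 and V3. For adherence, section 4.2 states the aim as: "Determine patient adherence to the ISC over the first six months: measured by I-CAS at V2 and V3".

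Section 9.2 makes two statements that matter here:
- On the adherence model: the V3 outcome is to be modelled by the same regressions as catheter choice, and the covariate list reads "with clinical and socio-demographic characteristics at V1, I-CAT score at V1, ICDQ score at V2, type of catheter chosen". ICDQ is the IC-Di-Q under its other abbreviation. Neither visit timing nor site is listed.
- On description: "The other secondary endpoints will be described at the different time points and according to the catheter type". All parameters are also to be described by gender. No split or adjustment by time since training is given.

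The visit date is recorded at all three visits (section 8). Section 9.2 also says that a statistical analysis plan will follow.

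**The concern.** Section 3 presents the first months as a learning and adaptation phase. It also says the IC-Di-Q is meant to follow patients' progress once solutions are in place, so the score is expected to move. A difficulty score at week 3 and one at week 12 then describe different stages, yet section 9.2 gives them the same meaning.

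Two results could suffer:
- In the V3 adherence model, the V2 difficulty score carries variation that comes only from the visit date. This blurs its link with later adherence.
- In the V2 tables, catheter types could appear to differ in difficulty, adherence or satisfaction because their users were seen at different times. That requires catheter mix and visit timing to vary together across sites. Section 6.2.1 requires only two types to be introduced, and section 3 names nurse's advice as a possible reason for choice, so catheter mix may well vary by site. The protocol does not say that it does.

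**Working it through.** **1. The plan's own figure.** The protocol gives no figure for V2 timing. Its one calculation, in section 9.1, uses half-width = 1.96 × √(p(1−p)/n).
- n = 250: 2.70% at p = 5% and 6.20% at p = 50% (stated ±2.75% and ±6.25%).
- n = 225 (10% lost): 2.85% and 6.53% (stated ±3.0% and ±6.5%).

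These agree with the plan. They concern choice criteria at V3, so V2 timing does not enter.

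**2. Width of the window.** 12 − 3 = 9 weeks, and 12 / 3 = 4, a fourfold range of time since training.

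**3. Is timing already covered by the text?** Section 9.2 has two covariate lists. The one for catheter choice is left open at its end. The one for V3 adherence is not: V1 characteristics, I-CAT at V1, ICDQ at V2, catheter type. As written, it takes in a score that depends on timing and leaves the timing out.

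**4. Effect on the V2 difficulty coefficient.** Assumptions, not taken from the documents: the score changes linearly by d SD from week 3 to week 12; the SD at any fixed week is 1; timing is otherwise unrelated to V3 adherence. Evenly spread visits add variance d²/12, and an even split between week 3 and week 12 adds d²/4. The coefficient is multiplied by 1 / (1 + added variance). This is the linear-model result, used here as an approximation for logistic regression.

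| d (SD) | Evenly spread: added variance → factor | Split at the extremes: added variance → factor |
|---|---|---|
| 0.25 | 0.0052 → 0.995 | 0.0156 → 0.985 |
| 0.5 | 0.0208 → 0.980 | 0.0625 → 0.941 |
| 1.0 | 0.0833 → 0.923 | 0.2500 → 0.800 |

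The loss is about 0.5% to 8% with evenly spread visits and 1.5% to 20% at the extremes.

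**5. Effect on V2 descriptions by catheter type.** Under the same drift, a gap of k weeks in mean V2 timing between two catheter groups creates a difference of d × k / 9. For k = 4 (assumed):
- d = 0.25: 0.25 × 4 / 9 = 0.11 SD
- d = 0.5: 0.5 × 4 / 9 = 0.22 SD
- d = 1.0: 1.0 × 4 / 9 = 0.44 SD

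For k = 0 the difference is 0 whatever the drift.

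**The case against.** The strongest reply is that a statistical analysis plan is promised, that derived visit days and timing tables commonly belong there, and that nothing in the protocol forbids them. Much of this stands: the window is legitimate routine care, and the protocol contains no contradiction or wrong figure here. It does not dispose of the point, because section 9.2 does not leave the adherence covariates open. It names them, includes a V2 score and omits its timing.

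A reader might infer more than the documents support:
- *That the adherence model ignores time since training altogether.* Its outcome is I-CAS at V3, around six months for all, with training at inclusion. Time since training at the outcome is roughly constant by design, so V2 timing enters only through the V2 difficulty covariate.
- *That catheter or site effects are confounded.* For catheter type this is possible but not stated. For sites, no comparison is planned, and the V2 results by catheter type are descriptive.
- *That change from V2 to V3 is distorted.* Taking six months as 26 weeks, the interval runs from 26 − 12 = 14 to 26 − 3 = 23 weeks. The synopsis mentions how adherence develops, but section 9.2 defines no change analysis.
- *That V2 follows 84 to 336 catheterisations* (3 × 7 × 4 and 12 × 7 × 4). Four per day is the minimum recommended frequency for eligibility, not the number performed, which the study itself measures.

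It can also be said that a main effect for timing corrects only a shift in mean score. If an early high score predicted adherence differently from a late one, an interaction would be needed. That is true and limits the remedy, but it is no reason to leave timing out.

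**Conclusion.** The point holds in a limited form. V2 scores from a window of 3 to 12 weeks, set by site practice, are pooled as one time point, and the stated covariates for V3 adherence include the V2 difficulty score without its timing. The coefficient for V2 difficulty may be somewhat attenuated: by a few per cent at moderate drift with evenly spread visits, and by 20% only with a 1 SD drift and every visit at week 3 or week 12. V2 descriptions by catheter type could reflect visit timing only if timing differs between catheter groups.

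Both sizes depend on an assumed linear drift of 0.25 to 1.0 SD, and the second also on an assumed 4-week gap. The documents supply neither. The analyses concerned are secondary and exploratory. The primary objective, N = 250 and its precision are unaffected. It is worth acting on because the correction needs no new data and is best fixed before the database freeze.

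**What to change.** Keep the routine-care window. In section 9.2, or in the analysis plan before the database freeze:
- Derive days from V1 to V2 from the recorded visit dates, and report their distribution overall and by catheter type. This shows directly whether a timing gap exists.
- Add days from V1 to V2 as a covariate beside ICDQ at V2 in the V3 adherence model.
- Present V2 IC-Di-Q, I-CAS and satisfaction by timing band, for example under 6 weeks and 6 to 12 weeks, as well as by catheter type.

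The cost is one model parameter and one further table, with no added visits, data items or patients. Crossing bands with three catheter types and two sexes gives 2 × 3 × 2 = 12 cells, on average 250 / 12 ≈ 21 patients each before any loss, so the table should be read as descriptive. The bands are not randomised groups. Section 7.3 withdraws patients who stop self-catheterisation, so the later band may be more selected.
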